- Clinically significant uncontrolled depression or severe psychiatric symptoms
- If subject has an established routine of inert vaginal lubricant use for routine or occasional relief of vulvar or vaginal symptoms prior to the study period, it may be continued during the

study period along with the study drug.

Study Design and Procedures

This will be a two-armed, randomized, open-label Phase II trial. All study subjects will be asked to fill out the simple 5-question BSSC-W. If any concern about sexual functioning is noted with the BSSC-W question 1 as a no answer to "are you satisfied with sexual function", the subject will also be asked to fill out the more extensive FSFI tool, to help determine which domain of sexual functioning is the most bothersome. Questions 7-10 on FSFI specifically assess degree of vaginal dryness while questions 17-19 assess pain with sex, which are both commonly associated with vaginal atrophy. Subjects who indicate that they are satisfied with their sexual function on BSSC-W in question 1 will be deemed ineligible for the study and will not complete the FSFI. All questionnaires will be administered in paper format.

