Additionally, at baseline, all study subjects will be asked to fill out the BSSC-W, QOL-CSV, and DHEA Trial Supplemental Clinical Survey. FSFI will also be completed at baseline by all subjects who indicate sexual complaints on Question 1 of the BSSC-W at baseline; any consented individuals who do not indicate sexual complaints on Question 1 of the BSSC-W at baseline will be considered a screen fail and will not complete the FSFI or continue in the study. Questionnaires will be administered in paper format. Subjects will be instructed not to use vaginal products other than water-based lubricants during intercourse throughout the duration of the study period. Subjects will be given a paper diary to record the dates and approximate times the treatment was used. Subjects will be advised to complete this at home. These diaries will be used to track compliance with study treatment. All adverse events (AEs) will be analyzed, tabulated and organized by organ-system and included in the primary analysis.

At 1 week (±3 days) from Day 1, Week 1, subjects will be followed up with via phone call to ensure study drug was received, emphasize study compliance with study treatment, remind subjects to correctly complete diary entries, and assess any changes in the subject's health.

At 6 weeks (±1 week) from Day 1, Week 1, subjects will be followed up with via phone call to emphasize study compliance with study treatment, remind subjects to correctly complete diary entries, and assess any changes in the subject's health.

Both follow-ups (1 week and 6 week) will be recorded/documented in eMR.

At 12 weeks (±1 week), from Day 1, Week 1, subjects will undergo a physical exam including clinical breast and gynecological exam. During gynecologic exams, the vaginal pH will be determined and a swab of vaginal epithelium sent to pathology to calculate the VMI. These will be used as objective physiologic markers to determine the improvement in vaginal atrophy. The cytologist's reading the specimens will be blinded.

Additionally, at 12 weeks (±1 week) from Day 1, Week 1, all study subjects will be asked to fill out the BSSC-W, QOL-CSV, and FSFI. Questionnaires will be administered in paper format. Diaries will be collected at the completion of study treatment, 12 weeks (±1 week) from Day 1, Week 1, or if treatment is not completed per protocol, when treatment is stopped.

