Protocol violation: a change to, or non-compliance with the IRB-approved procedures without prior Sponsor and IRB approval. Violation may affect health, safety, or rights of a subject. Any violation will be reported immediately to the Sponsor for guidance on reporting. Violations will be made available for Monitors to check against source data at each monitoring visit.

If the protocol deviation/protocol violation does not represent a significant alteration in the approved protocol and/or affect the safety or welfare of the subject, it will be reported to the UAMS IRB at the time of Continuing Review. If the protocol deviation or protocol violation represents a significant alteration in the approved protocol and/or if it affects the safety or welfare of the subject, it must be reported to the UAMS IRB immediately.

Compliance

All drug boxes and unused product will be collected from subject at last visit by research staff and will be given to the research pharmacy to log for compliance. No serious harm is anticipated from non-adherence or cessation of use of the investigational products.

Subject Withdrawal

Subjects may withdraw from treatment or consent from the study at any time for any reason, without penalty.

Subjects who voluntarily withdraw from study treatment will stop taking the study drug but will still participate in the research-related assessments. These research-related assessments include physical exam (including clinical breast and gynecological exam for pH and VMI), estradiol level, completion of BSSC-W, QOL-CSV, and FSFI, and reporting of AEs until the end of the study duration [i.e., Week 12 (±1 week)].

Subjects who withdraw consent from the study will stop taking the study drug and all research-related assessments will be ceased. Any data previously collected will be used but no further data will be collected following the subject's withdrawal of consent. Subjects will be encouraged to report AEs thought to be possibly/probably related to the study drug for 30 days after discontinuation.

For evaluation and reporting purposes, reasons for early withdrawal may be discussed with willing subjects for purposes of identifying potential problems with the drug or study design. When possible, subjects will be notified that any improvement in symptoms they perceived to be the

IRB 239531 Sponsor: UAMS Version 15 0/7/07/2023 Page 17 of 22

result of the study intervention may recede and a return to the pre-study baseline can be expected.

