The efficacy population will include all subjects with a baseline assessment who have received at least two weeks of treatment with either Intrarosa® or Replens™. Subjects who discontinue participation in the study (stop the assigned treatment, withdraw consent, etc.) before 2 weeks of treatment will not be included in the efficacy population. Subjects who discontinue participation in the study after 2 weeks but prior to 12 weeks will be included in the efficacy analysis. These subjects will be invited to complete the end of study evaluation at the time of discontinuation; these evaluation values will be included in the efficacy analyses.

The safety population will include all subjects who received at least one administration of either Intrarosa® or Replens™.

Efficacy Endpoints

The primary efficacy endpoint is VMI Response, which is defined as the change in the subject's calculated VMI from baseline to the end of treatment at 12 (±1 week).

Secondary efficacy endpoints: Secondary efficacy endpoints for all study subjects will be determined both at baseline and at the end of treatment. They consist of the following:

- Vaginal pH
- Dyspareunia and vaginal dryness scores on the BSSC-W and the FSFI,
- Quality of life using the QOL-CSV.

IRB 239531 Sponsor: UAMS Version 15 0/7/07/2023 Page 18 of 22

Analysis Plan

Descriptive Analysis: Each efficacy endpoint will be summarized by treatment group and time point as the mean, standard deviation (SD), minimum, 1st quartile, median, 3rd quartile, and maximum. Within each subject, the endpoint's response to treatment will be defined (and calculated) as the endpoint's value at 12 weeks minus its value at baseline; the resulting endpoint responses will be summarized by treatment group as the mean, SD, minimum, 1st quartile, median, 3rd quartile, and maximum. Graphical displays will consist of box plots and scatter plots along with profile plots, a.k.a. "spaghetti plots", that show how the individual subjects respond over time to their assigned treatment. Adherence to distributional assumptions will be assessed, and data transformation to increase such adherence will be implemented, if warranted.

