Appendix A: Study Calendar

	Pre- Study/Baseline ^a	Day1, Week 1 ^b	Week 2-12	End of Treatment ^c
Determine eligibility for study:	Χ			
Study consent discussed and signed	Χ			
Pregnancy test ^d	Χ			
Collect relevant disease-related data (mammogram, Pap				
smear)e, FSH levelf, baseline conditions, height, weight, and	X			
medical history				
Complete BSSC-W	Χg			Χg
Complete FSFI ^h	Χg			Χg
Complete DHEA Trial Clinical Supplemental Survey	Χg			
Physical exam (including gynecologic ⁱ and breast exams)	Χ			\mathbf{x}^{j}
Vaginal pH to be determined	Χ			X
Swab of vaginal epithelium collected and sent to pathology to calculate VMI ^k	X			х
Estradiol level ^l	Х			Х
Complete QOL-CSV	Χg			χg
Randomize to treatment arm	Χ			
Assigned treatment and study diaries dispensed to subject		Х		
Self-administration (starts same day as dispensed)				
Intrarosa® 6.5 mg insert nightly				
~OR~		x	x	
 Replens[™] 6.7 g prefilled applicator intravaginal two non- consecutive nights weekly 				
Collect AEs ^m		Х	Х	Х
Diary Submissions			Xn	Χo
Drug boxes and unused products collected from subject				Х
Follow up call			x ^p , ^q	

a Pre-study/Baseline should be completed within 28 days prior to Day 1, Week 1.

b Day 1, Week 1 visit may be done the same day as Pre-Study/Baseline visit if all Pre-Study/Baseline activities are completed and eligibility has been confirmed prior to Day 1, Week 1 activities.

c End of Treatment should be completed at week 12 from Day 1, Week 1, i.e., Week 12 ±1 week).

d Subjects who are post-menopausal will not require a pregnancy test. SoC pregnancy test results may be used if completed within 7 days of Day 1, Week 1.

e Mammogram (if deemed appropriate by the treating physician) and normal Pap must be documented within 12 months prior to study entry. If these are not documented in the medical history, they will be obtained for the study. SoC Pap and mammogram (if appropriate) may be used if completed within 28 days of Day 1, Week 1. Pap is not required for females whose cervix has been removed by surgery for reasons not related to cervical cancer or serious cervical pre-cancer.

f If FSH level is not documented in the medical history, one will be obtained prior to study entry.

g Should be completed in-person but can be completed over the phone, if necessary.

h FSFI is to be completed only if participant answers no to question 1 on the coinciding BSSC-W.

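### A Study Calendar footnote makes the 12-week FSFI conditional on dissatisfaction at that visit, while the protocol body collects it from every subject

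*Combined protocol and SAP*

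**What the plan says.** Four parts of the combined protocol and SAP bear on who completes the FSFI at Week 12.

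- **Appendix A: Study Calendar, footnote h.** "FSFI is to be completed only if participant answers no to question 1 on the coinciding BSSC-W". The footnote mark is on the row label, and the row is ticked at Pre-Study/Baseline and at End of Treatment.
- **Study Design and Procedures.** At baseline the FSFI depends on Question 1 of the BSSC-W, and "any consented individuals who do not indicate sexual complaints on Question 1 of the BSSC-W at baseline will be considered a screen fail". The opening paragraph of the section agrees: "Subjects who indicate that they are satisfied with their sexual function on BSSC-W in question 1 will be deemed ineligible for the study". At 12 weeks there is no condition: "all study subjects will be asked to fill out the BSSC-W, QOL-CSV, and FSFI".
- **Subject Withdrawal.** Women who stop treatment but stay in follow-up have their assessments listed without a Question 1 condition: "completion of BSSC-W, QOL-CSV, and FSFI, and reporting of AEs until the end of the study duration".
- **Efficacy Endpoints.** "Secondary efficacy endpoints for all study subjects will be determined both at baseline and at the end of treatment", and the list includes "Dyspareunia and vaginal dryness scores on the BSSC-W and the FSFI".

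The Analysis Plan defines response as the 12-week value less the baseline value and uses the 12-week value as the ANCOVA outcome. Secondary tests are one-sided at 0.01.

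**The concern.** For a woman who reports satisfaction at Week 12, one text requires the FSFI and the other withholds it. Staff cannot follow both, and no section says which governs.

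If staff work from the calendar, that woman has no Week-12 FSFI. She then drops out of the change-score, Week-12 and ANCOVA comparisons for the FSFI scores. This is not ordinary dropout. The protocol itself would select subjects on an answer given after randomisation, about the domain that the FSFI measures, in a trial described as follows: "This will be a two-armed, randomized, open-label Phase II trial". The women removed could be those who improved most. The Data Analysis section uses end-of-study values taken at discontinuation for women who stop after two weeks, but it has no provision for a completer whose FSFI was skipped.

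**Working it through.** **1. Can footnote h be read as baseline-only?** No, for two reasons. The mark is on a row that is ticked at End of Treatment, and the wording ties each FSFI to the BSSC-W of the same visit.

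**2. Where does it act?** Dissatisfaction on Question 1 is an inclusion criterion, so every enrolled woman has answered no at baseline. There the footnote agrees with the body text and removes nobody who is enrolled. Among enrolled women it can act only at End of Treatment.

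**3. Direct loss.** With 30 per arm, a share *q* satisfied at Week 12 removes 30*q* FSFI outcomes: 10% gives 30 × 0.10 = 3, and 20% gives 6.

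**4. Check of the power method.** For a one-sided two-sample t-test, the noncentrality is d√(n₁n₂/(n₁+n₂)) with n₁+n₂−2 degrees of freedom. The plan's VMI figures at α = 0.05 reproduce:
- 30 per arm: 0.8 × √15 = 3.098, power 92.2% (stated 92.2%).
- 24 per arm: 0.8 × √12 = 2.771, power 86.1% (stated 86.1%).

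**5. Illustration for the FSFI.** The documents give no FSFI effect size, satisfaction rate, correlation or power claim, so every input here is an assumption. I take a true difference of 0.8 SD (borrowed from the VMI planning value), 30 per arm and one-sided α = 0.01. With full collection, power is 75.8%.

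Let FSFI change be N(0,1) on Replens and N(0.8,1) on Intrarosa. Let latent satisfaction have within-arm correlation *r* with that change. A woman is satisfied, and so removed, if her standardised latent score exceeds *a*. With λ = φ(a)/Φ(a), the women who remain have:
- mean change μ − rλ
- variance 1 − r²(aλ + λ²)

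Case (a), r = 0.5, 20% of Replens women satisfied, treatment acting on satisfaction only through the FSFI:
- Replens: a = 0.842, λ = 0.350, mean 0 − 0.5 × 0.350 = −0.175, variance 0.896, n = 24.0.
- Intrarosa: a = 0.842 − 0.5 × 0.8 = 0.442, so 32.9% are satisfied; λ = 0.540, mean 0.8 − 0.5 × 0.540 = 0.530, variance 0.868, n = 20.1.
- Difference 0.530 + 0.175 = 0.705 SD, and 0.705/0.8 = 88% of the truth.
- Pooled SD 0.940, noncentrality (0.705/0.940) × √(24.0 × 20.1/44.1) = 2.48, power 53.0%. The same sample sizes without selection give 59.3%.

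Other cases by the same formulas:

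| Case | r | Satisfied, Replens / Intrarosa | Difference (SD) | Share of truth | Power |
|---|---|---|---|---|---|
| (b) | 0.5 | 20% / 20% | 0.80 | 100% | 69.7% |
| (c) | 0.5 | 20% / 10% | 0.88 | 110% | 80.4% |
| (d) as (a), fewer satisfied | 0.3–0.5 | 2–5% on Replens | 0.75–0.79 | 94–99% | 69–74% |

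With no true effect and r = 0.5, the 20%/10% pattern produces a spurious difference of 0.175 − 0.0975 = +0.077 SD and a false-positive rate of 2.0% instead of 1%. The 20%/20% pattern keeps it at 1.0%. With 20% of Replens and 30% of Intrarosa women satisfied it falls to 0.5%. Simulation gave the same results to within about 0.01.

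**The case against.** The strongest reply is that the intended rule is hardly in doubt. The 12-week visit text, the withdrawal section and the endpoint definition are all unconditional at the end of the study, and so is the hypothesis paragraph under Objectives and Rationale, which has the inventories given before and after the study period. Against them stands one footnote in an appendix that the body calls a summary. It looks like the screening gate carried over to the wrong visit, which would make this a clerical slip. Harm also needs staff to prefer the footnote and women to become satisfied, and the documents give neither frequency.

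Much of this stands. The weight of the text favours unconditional collection, and the likelihood of harm is unknown. It does not remove the conflict: the footnote is an explicit visit-level rule in the table that staff may work from, and no statement of precedence overrides it.

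Three narrower points also stand:
- The illustration treats FSFI change as a single variable, whereas the endpoints are dyspareunia and dryness scores whose correlation with overall satisfaction is unknown.
- A skipped FSFI could be taken after the visit window and logged as a deviation; it would be late rather than impossible.
- Footnote h does not restrict the BSSC-W, but that form is not reproduced, so it cannot be confirmed that a satisfied woman goes on to answer its later items.

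**Conclusion.** The concern holds. The Study Calendar and the 12-week visit text contradict each other, and following the calendar would deplete the FSFI secondary comparisons and could bias them.

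The certain part of the size is 3 of 30 outcomes lost for each 10% of an arm satisfied, and nothing if no woman becomes satisfied. If satisfaction rises with FSFI improvement, the direction of bias depends on the arms:
- toward zero if more Intrarosa women are satisfied;
- little or none if the rates are equal;
- away from zero if more Replens women are satisfied.

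Question 1 asks about overall satisfaction and the trial is open-label, so the pattern cannot be assumed. The power and bias figures rest wholly on assumed inputs and only show scale.

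The primary endpoint, the planned sample size and the stated power are unaffected, and footnote h does not restrict collection of vaginal pH, the QOL-CSV or the BSSC-W. This should be fixed because the text is wrong as written and the repair is cheap.

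**What to change.** Limit the condition in footnote h to baseline. Suggested wording: *At baseline, the FSFI is completed by subjects who answer no to BSSC-W Question 1; others are screen failures. At End of Treatment, all subjects complete the FSFI whatever their BSSC-W answer.* This matches the 12-week visit text and is consistent with the withdrawal and endpoint sections.

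If Week-12 visits have already taken place, report by arm how many FSFIs were skipped under the footnote. Obtain by phone any still inside the ±1-week window, which footnote g allows. A bounds-type sensitivity analysis for the rest is worth adding, although with about 30 per arm the bounds may be wide.

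The cost is one footnote in an amendment, a reminder to staff, and a few minutes of questionnaire time for women who report satisfaction at Week 12.

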Appendix B. Eligibility Flow Diagram

[figure not shown]
Postmenopausal breast cancer survivors who have completed primary treatment with curative intent and are on AI for > 6 months with vaginal symptoms identified at UAMS Cancer and Women's Health Clinics and CARTI Cancer Center.

EXCLUSION CRITERIA:

- Use of any estrogen or progesterone depot preparation or progestin implant, androgen or anabolic steroids, or natural over-the-counter estrogenic products without 6-month washout period
- Use of any oral or transdermal hormonal products (estrogen, progestin, or DHEA), or vaginal or intrauterine hormonal products without 6-month washout period
- Concomitant vulvar and vaginal surgical or laser treatments
- Vaginal infection or confounding vulvar or active vaginal disease process
- Active malignant breast or gynecologic disease
- History of radiation to the pelvis or prior gynecologic cancer or pre-cancer
- Inability to tolerate a vaginal/speculum exam
- Undiagnosed persistent or recurring genital bleeding or other indication of active pelvic disease process
- Clinically significant uncontrolled depression or severe psychiatric symptoms

INCLUSION CRITERIA:

- Females, ages 18-70
- Postmenopausal patients with a history of breast cancer who have completed primary treatment with curative intent and currently are on an Al and have been for ≥6 months
- DCIS or Stage I-III, hormone-receptor positive breast cancer regardless of HER2 status
- Postmenopause defined as ≥ 12 months spontaneous amenorrhea, ≥ 6 months spontaneous amenorrhea with serum FSH levels > 40 mlU/mL, or ≥ 6 weeks postsurgical bilateral oophorectomy with or without hysterectomy
- Reported dissatisfaction with sexual function on Question 1 of the BSSC-W
- No planned changes in Al during the study period
- Mammogram within 12 months prior to study entry (if deemed appropriate by the treating physician)
- Normal Pap within 12 months prior to study entry (i.e. negative Pap results consistent with ACS guidelines).
 Females whose cervix has been removed by surgery for reasons not related to cervical cancer or serious cervical pre-cancer (e.g., CIN 2 or 3 (HSIL, moderate or severe dysplasia) or AIS) may be excluded from this requirement.

Note: Thirty subjects/arm (60 subjects) give the 1-sided Student's t-test 92.2% power at α = 0.05 to detect a 0.8-SD increase in VMI Response with Intrarosa® compared to Replens™. Under 20% attrition, the remaining 24 subject/arm (48 subjects) still provide the 1-sided Student's t-test with 86.1% power at α = 0.05 to detect the 0.8-SD increase in VMI Response.
